This project presents an innovative proposal, addressing a BCG vaccine with known efficacy against severe TB in childhood and reliable for the use of adjuvant therapy in patients with malignant bladder neoplasia.

BCG is an easily accessible vaccine, widely used by SUS in newborn children, thus facilitating its incorporation into a new preventive proposal for COVID-19. In addition, the selection of health professionals will be based on diagnostic screening and confirmatory tests of COVID-19.

It is intended to analyze the role of BCG in the prevention of infection and also in the occurrence of severe forms of COVID-19 in addition to evaluating the immune response mediated by this vaccine in voluntary health professionals.

GOALS:

In the period of 6 months, to analyze the effect of BCG as a protective factor for COVID-19 in research volunteers, aiming at greater efficiency in the prevention of subjects at high risk of infection and evolution to severe forms of the disease, as well as to evaluate the specific and non-specific immune responses to SARS-CoV-2 in vaccinated and unvaccinated volunteers who evolved with COVID-19 or not.

Primary Objectives:

1. Assess the impact of BCG vaccine administration on the cumulative incidence of SARS-CoV-2 infection
2. Assess the impact of BCG vaccine administration on the cumulative incidence of severe forms of COVID-19
3. Evaluate the bcg vaccine-mediated immune response in volunteers

Secondary Objectives:

In groups receiving BCG or placebo, infected and not infected with SARS-CoV-2:

- Epidemiological:

1. Estimate whether BCG vaccination compared to placebo prolongs the time to the first respiratory disease proven by SARS-CoV-2;
2. Estimate whether BCG vaccination compared with placebo reduces the proportion of symptoms associated with COVID-19 (fever or at least one sign/symptom of respiratory disease);
3. Estimate whether BCG vaccination compared to placebo reduces absenteeism (missing days) in volunteers who are health professionals;
4. Analyze the safety of BCG vaccination in adult volunteers;

- Laboratories:

5. Describe the inflammatory profile by dosing neutrophils, platelets, cit-H3, alpha 1 antitrypsin (α 1AT), galectin-2, ferritin, transferrin-R, glycated hemoglobin (HbA1c),

C-reactive protein (CRP), D-dummer, LDH, albumin and hemosedimentation velocity (ESR);

6. Describe the profile of inflammatory cytokines identified in the BCG and placebo groups, comparing to the protective events to SARS-CoV-2;

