Randomly eligible participants who have provided informed written consent will be recruited. Participants will then be allocated to one of the study regimens in a ratio of 1:1.

1. **Intervention:** BCG vaccine, single dose
2. **Control regimen:** placebo, single dose.

In the BCG clinical trial, participation in the study will last 6 months: during the first 4 months, or for the duration of the recruitment period, participants will receive the randomly designated BCG regimen or only control group. After the recruitment period, all study participants should have received BCG or placebo, and both groups will be monitored through clinical and laboratory examination for 6 months of follow-up. Biosafety care to combat COVID-19 adopted in the participating Health Units will also be monitored during the study period.

Comparator:

The natural evolution of SARS-CoV-2 infection in health professionals will be used to evaluate the efficacy of bcg use as preventive therapy, considering the use of specific vaccines against COVID-19, the time of positivity of COVID-19 tests and the evolution to severe forms of COVID-19.

Specific vaccines against SARS-CoV-2:

- Coronavac® (Sinovac® / Butantan Institute):

The vaccine developed by the Sinovac laboratory® in partnership with the Butantan Institute is a vaccine containing the inactivated SARS-CoV-2 virus. Seroconversion studies of the Sinovac/Butantan vaccine showed results of >92% in participants who took both doses of the vaccine within 14 days and > 97% in participants who took both doses of the vaccine within 28 days.

The efficacy of this vaccine was demonstrated in a regimen containing 2 doses with an interval of 2 weeks. For the prevention of symptomatic cases of COVID-19 that required outpatient or hospital care, efficacy was 77.96%. There were no serious cases in vaccinated subjects, compared to 7 severe cases in the placebo group.

Considering the absence of co-administration studies, covid-19 vaccines are currently not recommended simultaneously with other vaccines. Thus, a minimum interval of 14

days is recommended between COVID-19 vaccines and the different vaccines of the National Vaccination Calendar.

- Covishield® (AstraZeneca® / Fiocruz):

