These analyses will be performed at the defined times of collection and evaluation of the study groups. The markers to be studied in cell populations will be:

Lymphocyte T: CD3, CD4, CD119, IL-12R β 2, IFN- γ , TNF- α , IL-4, IL-10, IL-13, IL-21, IL-1RI, IL-6R α , IL-17A, IL-17F, IL-22, FoxP3, CD25, Galectin-3, IL-35, TGF- β .

Neutrophil: CCL22, CD169, CD68, ZAP70, CD11b, CD11c, LDH, CD64, IL-17.

Monocytes: CD14, CD11c, HLA-DR, CD45, IP-10, MIP-1 α , MIF.

Inflammatory and metabolic profiles will be measured by luminex, using serum from patients for the panel: IFN- α 2, IFN- γ , IL-10, -12 p40, -12 p70, -13, -15, -1 Ra, -1 α , -1 β , -2, -4, -6, -8, -23, -17, -18, -22, MIP-1 α , MIP-1 β , TNF- α , VEGF-A, Adiponectin, Hepcidine, Insulin, MMP-1, -2, -8, -9, MIF, Glucagon, Greeline, Leptin, CD163s, Galectin-1 and -3, Vitamin D protein, PCR, albumin, citrulinada histona H3, alpha1-anti-trypsin, P-selectin, D-dummer, PSGL-1, tPA, CD40L, PAI-1, Tissue Factor IX, CXCL8 (IL-8).

Transcriptoma

RNA obtained from peripheral blood cells will be used to evaluate the signaling pathways of monocytes and neutrophils in both study groups. RNA sequencing (RNASeq) will be used to evaluate the profiles, according to the manufacturer's instruction (Illumina).

Laboratory procedures to be performed at each research center:

Laboratory procedures will be different according to the research center where the participant is included, as follows:

	Recrutamento	Inclusão ou M0	M1	M3	M6	M9	M12	COVID suspeito ou confirmado	14 – 30 dias após COVID-19 suspeito ou confirmado
HUCFF-IDT UFRJ	RT-PCR Coronavírus swab NF, sorologia Coronavírus, Dosagem BHCG, sorologia anti HIV	IGRA, análises clínicas, biomarcadores	Sorologia Coronavírus, análises clínicas, biomarcadores	Sorologia Coronavírus	Sorologia Coronavírus	Sorologia Coronavírus	Sorologia Coronavírus	RT-PCR Coronavírus swab NF	Sorologia Coronavírus, análises clínicas, biomarcadores
HUPE-PPC UERJ	RT-PCR Coronavírus swab NF, sorologia Coronavírus, Dosagem BHCG, sorologia anti HIV	IGRA, análises clínicas, biomarcadores	Sorologia Coronavírus, análises clínicas, biomarcadores	Sorologia Coronavírus	Sorologia Coronavírus	Sorologia Coronavírus	Sorologia Coronavírus	RT-PCR Coronavírus swab NF	Sorologia Coronavírus, análises clínicas, biomarcadores

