According to CNS Resolution No. 441 of 2011 (Art. 1) and Ordinance MS No. 2,201 of 2011 (Art. 3), any organized collection of human biological material collected for scientific research purposes, including samples intended for routine examinations in a clinical trial (e.g., blood count and renal function) are considered as constituents of a biorepository or biobank. The biological material will be used as provided for in the research protocol, with no further future analyses different from those foreseen. If there is a proposal for future use of the stored samples, approval in the CEP/CONEP system will be required and a new protocol and TCLE will be submitted so that each participant can choose whether or not to allow the use of the samples for future studies.

Statistical Analysis Plan:

The primary efficacy analysis will compare the cumulative incidence of SARS-CoV-2 infection and the cumulative incidence of severe forms of COVID-19.

These analyses will occur when the last enrolled research subject has completed 30 days and 6 months of preventive treatment and will be performed using the results of COVID-19 diagnostic tests, as well as the data available in participating hospitals and national electronic notification systems of COVID-19. A modified treatment intention analysis (MITT) and protocol (PP) will be performed. The safety and tolerability analysis will consist of all patients who have been randomized and received a dose of the vaccine or placebo. Based on serum immune response concentrations, we will calculate certain immunoinflammatory variables related to the use of BCG versus placebo among subjects infected and not infected by COVID-19 among the categories with COVID-19 vaccine (Coronavac® or Covishield®) and without covid-19 vaccine.

The intervention and control groups will be compared at the time of inclusion in the study in relation to sociodemographic, clinical, radiological and biochemical imaging variables, in order to evaluate the adequacy of the randomization process. Multivariate

analyses using logistic regression or Poisson models with robust variance will be used to evaluate the effect of BCG vaccine on primary and secondary outcomes. Associations will be expressed in the form of risk ratios and respective 95% confidence intervals. Data imputation may be required and the *random forest system* will be used. Statistical software R, version 10.0.

Sample size:

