It is estimated that it will take 376 individuals in each of the comparison groups to ensure a statistical power of 80% and a type I error of 5%, considering an incidence of SARS-CoV-2 infection of 20% in BCG vaccinated, 30% in unvaccinated, 15% in covid-19 vaccinated. It is expected a reduction in the joint effect of BCG with the COVID-19 vaccine between 10% and 15% and that the percentage of people vaccinated with BCG in the cohort is 50% and the percentage of people vaccinated for Covid-19 in the cohort is 80%.

We will also use for the two outcomes (below) the sequential design the groups are followed up until there is a group with clear benefits or that both groups do not present difference. This design is used when the results need to be known very quickly. If there is a large difference between the treatments, then this study will be performed in a shorter time when compared to the parallel trial. The main ethical advantage is that if one treatment shows a superiority over the other, the study can already be stopped. However, the interim analyses will be previously planned, in such a way that the calculation of sample size allows the multiplicity of the tests. The meaning of p-values in sequential analyses also changes, because when using sequential analyses, more than one analysis is performed, and the typical definition of a p-value as data "at least as extreme" as observed needs to be reset. One solution is to sort the p-values of a series of sequential tests based on the downtime and at what time the test statistic was in a certain appearance, known as ordering.

OUTCOMES:

Primary Outcome

1. Compare the cumulative incidence of SARS-CoV-2 infection

It is estimated that it will take 376 individuals in each of the comparison groups to ensure a statistical power of 80% for the detection of a difference in effects of 10%, considering that the control group will have an accumulated incidence of SARS-CoV-2 infection of 30% after 6 months of follow-up, for a type I error of 5%.

2. Compare the cumulative incidence of severe forms of COVID-19

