We will also use for the two outcomes the sequential design the groups are followed up until there is a group with clear benefits or that both groups do not present difference. This design is used when the results need to be known very quickly. If there is a large difference between the treatments, then this study will be performed in a shorter time when compared to the parallel trial. The main ethical advantage is that if one treatment shows a superiority over the other, the study can already be stopped. However, the

interim analyses will be previously planned, in such a way that the calculation of sample size allows the multiplicity of the tests. The meaning of p-values in sequential analyses also changes, because when using sequential analyses, more than one analysis is performed, and the typical definition of a p-value as data "at least as extreme" as observed needs to be reset. One solution is to sort the p-values of a series of sequential tests based on the downtime and at what time the test statistic was in a certain appearance, known as ordering.

3. Assess the BCG vaccine-mediated immune response in healthcare professionals

SARS-CoV2 infection is estimated to occur in approximately 20% of health professionals vaccinated by BCG (experimental group), in 30% of health professionals not vaccinated by BCG (placebo group) and not vaccinated for COVID-19 and in 15% in COVID-19 vaccinated without BCG vaccine. A reduction of 10% to 15% of the joint effect of bcg vaccine with Covid-19 vaccine is expected.

In this scenario, with the bearing of 376 health professionals in each arm, if we assume that the percentage of covid-19 vaccinated is 80% and equal in each arm, SARS-CoV2 infection is expected to be detected in 15 professionals vaccinated only with BCG, in 23 professionals not vaccinated with BCG and COVID-19 vaccine, 45 professionals vaccinated for COVID-19 without bcg vaccine and 38 professionals vaccinated for COVID-19 and BCG. For each subgroup (vaccinated and not vaccinated with BCG) it will be possible to identify the predictive biomarkers of infection by comparing infected professionals with those who were not infected with SARS-CoV2.

INTERIM ANALYSIS PLAN:

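### Primary outcome 3, the immune response to BCG, designates no marker or visit to decide BCG versus placebo and has no multiplicity control

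*Combined protocol and SAP*

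**What the plan says.** Primary objective 3 is to "Evaluate the bcg vaccine-mediated immune response in volunteers". Item 3 under Primary Outcome reads "Assess the BCG vaccine-mediated immune response in healthcare professionals".

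The text beneath that outcome gives expected infection counts and a search for predictors of infection, comparing infected with uninfected people within each BCG group. It describes no immune contrast between BCG and placebo.

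That contrast appears only in the Statistical Analysis Plan: "we will calculate certain immunoinflammatory variables related to the use of BCG versus placebo", among infected and uninfected people and by COVID-19 vaccine category. The variables are not identified.

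Candidate markers stand elsewhere:

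- **Immunoassays** names five (cit-H3, alpha 1 antitrypsin, D-dimer, LDH and CRP) at M0, M1, M3 and M12.
- **The inflammatory profile section** adds cell-marker panels and a long serum list: "Inflammatory and metabolic profiles will be measured by luminex, using serum from patients for the panel". RNA sequencing follows under Transcriptoma.
- **Secondary objectives** 5, 6, 8 and 12 cover inflammatory markers, cytokines, cell populations and transcriptomics. All five Immunoassays markers appear in secondary objective 5.

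The Study visits table schedules biomarkers at M0, at M1 and 14 to 30 days after the onset of COVID-19 symptoms, at two of the three centres.

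**The concern.** A primary outcome should fix in advance what result would count as a finding. Here the choice of marker, visit and test is open, and no rule controls the error across the choices. If the candidates are tested one by one and any significant one is taken to meet the outcome, the error rate exceeds 5% by an amount set by how many are tried. A claim that BCG changed immunity could then rest on whichever marker happened to differ.

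The split by infection is a second weakness. Infection happens after randomisation and may itself be affected by BCG. Comparing arms among the infected, or among the uninfected, is therefore not a comparison that randomisation protects.

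**Working it through.** **1. The plan's own figures under outcome 3.** The section takes 376 per arm and says "if we assume that the percentage of covid-19 vaccinated is 80% and equal in each arm". With its infection rates:

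- BCG only: 376 × 0.2 × 0.20 = 15.0 (plan: 15)
- neither vaccine: 376 × 0.2 × 0.30 = 22.6 (plan: 23)
- COVID-19 vaccine only: 376 × 0.8 × 0.15 = 45.1 (plan: 45)
- both: 376 × 0.8 × 0.15 × 0.85 = 38.4 (plan: 38, using a 15% relative reduction)

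All four reproduce. They are infection counts; none concerns a marker difference between arms.

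**2. Number of candidates.** Immunoassays gives 5. The Luminex list gives 48 distinct serum analytes, counting IL-8 and CXCL8 once and Tissue Factor IX as one entry. The cell panels add 20 + 9 + 7 = 36 entries, which are not used below.

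**3. Assumptions.** The plan states no test for these markers. I assume a two-sided 5% test of each marker at one visit (M1), no adjustment and no true effect. The correlation between markers is not in the documents, so a range is shown.

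**4. Formulas.** For k independent tests, the chance of at least one false positive is 1 − 0.95^k.

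- k = 5: 1 − 0.774 = 22.6%
- k = 48: 1 − 0.085 = 91.5%

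For correlated tests, each statistic is √ρ·G + √(1 − ρ)·E, where G is a shared standard normal and E is a separate one for each marker. I counted how often the largest absolute value exceeds 1.96 in 200,000 simulated draws.

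| Correlation ρ | 5 markers | 48 analytes |
|---|---|---|
| 0 (exact) | 22.6% | 91.5% |
| 0.3 | 20.8% | 79.6% |
| 0.5 | 18.4% | 61.5% |
| 0.7 | 14.8% | 39.8% |
| 0.9 | 10.2% | 19.2% |

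The expected number of false positives is 5 × 0.05 = 0.25 or 48 × 0.05 = 2.4, whatever the correlation.

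**5. Sampling times.** Immunoassays lists M3 and M12. The Study visits table has antibody levels only at M3, and follow-up ends at M6. The laboratory table by centre has an M12 column, but with coronavirus serology only. M1 is thus the only scheduled post-dose biomarker visit for all participants at the two biomarker centres.

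**6. After the change.** One designated marker at M1 has a 5% false-positive chance. For scale, Bonferroni over 48 analytes would use 0.05/48 = 0.00104 each and give 1 − (1 − 0.00104)^48 = 4.9% overall.

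**The case against.** The strongest defence is that outcome 3 is primary in name only. Study Design places the inflammatory profile in an observational study of two cohorts. The Statistical Analysis Plan confines the primary efficacy analysis to infection and severe COVID-19, and the Interim Analysis Plan leaves markers out. Cytokines, cell populations and transcriptomics are expressly secondary. The 95% intervals in the plan belong to risk ratios, which do not fit concentrations without a cut-off, so no 5% test per marker is actually stated.

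Much of this stands, and it limits the point. It does not answer it: two sections still call the outcome primary, the model sentence covers primary and secondary outcomes alike, and nothing says what decides this one.

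Four stronger readings are tempting but not supported:

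- **That the plan names no marker or visit.** Immunoassays names five markers and four times. What is missing is a designation for outcome 3.
- **That a chance positive is likely whatever is done.** That depends on the list used and the correlation. Five markers at M1 give 15% to 23%, and even 48 analytes fall below one half at correlation 0.7.
- **That 48 analytes in 4 to 6 strata make 192 to 288 tests at M1.** Participants must be RT-PCR negative at entry, and seronegative too unless already COVID-vaccinated. Ten days after dosing the infected strata would be nearly empty. Samples after COVID-19 come 14 to 30 days after symptom onset.
- **That the efficacy conclusions are inflated by this.** Outcomes 1 and 2 and the interim analysis do not use these markers.

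**Conclusion.** The point holds for outcome 3 alone. No marker or visit is designated to decide the randomised immune comparison, no test is stated, and nothing controls error over the candidates. Under unadjusted two-sided 5% tests at M1 with no true effect, the chance of at least one false positive is about 15% to 23% for the short list and 40% to 91.5% for the serum panel (correlation 0.7 to 0), with 19% for the panel at 0.9. That is roughly 3 to 4.5 times the nominal 5% for the short list and 8 to 18 times for the panel over the 0.7 to 0 range. The 5% tests, the correlations and the use of either list as the test family are my assumptions, because the plan leaves them open. The sponsor should settle this before unblinding.

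**What to change.** In Primary Objectives, the Statistical Analysis Plan and item 3 under Primary Outcome:

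1. Label the immune response exploratory.
2. Analyse the BCG-minus-placebo difference at M1 in whole arms at the two biomarker centres, not within infection groups, for every measured analyte. State a model suited to concentrations.
3. Apply Benjamini-Hochberg control of the false discovery rate at 5% across the full set, and report every analyte.

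If the sponsor wants it to stay primary, name one marker or one fixed composite score at M1 before unblinding as the only deciding contrast, and treat the rest as exploratory.

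Separately, reconcile the M3 and M12 times in Immunoassays with the Study visits table and the 6-month follow-up.

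The cost is wording and a routine adjustment, with no new samples. The downside is that fewer individual markers will be declared significant.

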Participants who present some test results collected during the study outside the normal range will be evaluated by the study physician. It should be indicated in the participant's folder that this result has been verified and whether or not there is clinical significance. If any, the participant should be referred for specialist evaluation at the hospital where his follow-up is being carried out.

Visits	Evaluations	Exams	Procedures
Screening or Recruitment	Face-to-face assessment of eligibility criteria, application of the TCLE	NASOarchyeal swab RT-PCR, anti-SARS-Cov-2 antibody levels, BHCG dosage and HIV serology	Invitation to participate in the study, application of the TCLE, collection of clinical samples (nasopharangeal swab and blood).
Inclusion or M0 0 day of preventive treatment (ToT) (BCG or placebo)	Face-to-face assessment with confirmation of eligibility, clinical inclusion visit, collection of exams and dose of BCG or placebo	IGRA; Complete blood count, lipidogram, albumin, HbGlic, LDH, PCR, ESR, D-D-Dmer; and biomarkers*.	Nursing and medical consultation. Collection of clinical sample (blood). Application of preventive treatment.
S1 - S12 7-90 days of preventive TTO (±3 days)	Telephone and/or SMS contact, and/or weekly email and sending photo of the injection site	No exams	Fever questionnaires and/or respiratory signs and symptoms and photo submission of the injection site
M1 10 days of preventive TTO (±5 days)	Face-to-face visit to the laboratory for blood collection for biomarkers	Anti-Anti-SARS-Cov-2 antibody levels; Complete blood count, lipidogram, albumin, HbGlic, LDH, PCR, ESR, D-D-Dmer; and biomarkers*.	Collection of clinical sample (blood).
M3 90 days of preventive TTO (±14 days)	Face-to-face clinical visit for follow-up and blood collection for serology	Anti-Anti-SARS-Cov-2 antibody levels	Nursing and/or medical consultation. Collection of clinical sample (blood).
M4/M5 120/150 days of preventive Tom (±14 days)	Telephone contact and/or SMS, and/or weekly email	No exams	Fever questionnaires and/or respiratory signs and symptoms
M6 180 days of preventive TTO (±14 days)	Face-to-face clinical visit to close the study and for blood collection for serology	Anti-Antibody levels anti-SARS-Cov-2.	Nursing consultation. Collection of clinical sample (blood).
Fever and/or respiratory signs and symptoms	Face-to-face visit to the Worker's Health sector of its study center to collect exams	RT-PCR	Clinical sample collection (swab and blood).

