	Face-to-face clinical visit to the study center since asymptomatic and 14 – 30 days after the onset of symptoms	Anti-Anti-SARS-Cov-2 antibody levels; Complete blood count, lipidogram, albumin, HbGlic, LDH, PCR, VHS, D-Dallin and biomarkers*.	Nursing or medical consultation. Copy of the tests performed during COVID-19 infection. Collection of clinical sample (blood).

Subtitles: M0: Moment zero; S1-S12: Weeks 1 to 12; M1: Moment 1; M3: Month 3; M4: Month 4, M5: Month 5; M6: Month 6; *Clinical Analyses and Biomarkers: Will be performed only in hucff-idt ufrj, HUPE-PPC UERJ centers.

Storage of specimens during study visits:

The nasopharinal swab will be *obtained for the realization of the real time – polymerase chain reaction* (RT-PCR) for COVID-19. The collection will be performed using the technique described in the Manual of the Ministry of Health. The collection should be performed with the rubbing of the swab in the posterior region of the nasal caress trying to obtain some of the mucosal cells. The swab will be stored in 15ml tubes containing DMEM + Fetal Bovine Serum 10% + L-Glutamine Solution–Penicillin–Streptomycin.

After collection, the specimen will be packed in a refrigerator of specimens from the research center with temperature control between 2 - 8 °C.

Blood collection will comply with the guidelines of the Ministry of Health in the Manual Techniques for Blood Collection (2001) for the performance of blood count, lipidogram, albumin, LDH, ESR, C-reactive protein, D-dimmer and dosage of biomarkers described in the study protocol. The collected material will be distributed in 11 blood tubes [1 SST tube, 2 EDTA tubes – purple cap (4.5ml/each), 1 serum tube - red cap (4 ml/each), 1 gel activator tube - yellow cap (4 ml/each), 2 tubes with soric heparin - green cap (8 ml/each) and 1 Tempus tube – blue cap (3 ml/each)]. During the *screening or recruitment* visit, blood will be collected for BHCG dosage and HIV serology. In the inclusion visit the material will also be sent for IGRA [4 tubes Kit IGRA (1ml/each)].

After collection, the specimen will be packed in a refrigerator of specimens from the research center with temperature control between 2 - 8 °C.

All specimens will be delivered to their destination laboratories, transported in thermal boxes maintaining the necessary refrigeration and obeying the criteria of storage and maintenance of the viability of the collected material.

Procedure for applying bcg or placebo vaccine:

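### Primary objective 3 has no whole-arm randomised analysis: the only immune-specific BCG-versus-placebo comparison is split by infection, a post-randomisation outcome, and by COVID-vaccine category

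*Combined protocol and SAP*

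**What the plan says.** Primary objective 3 is: "Evaluate the bcg vaccine-mediated immune response in volunteers". It appears again as item 3 under Primary Outcome. Neither place names a marker, a visit, a contrast or an effect size.

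The Statistical Analysis Plan gives it one sentence: "we will calculate certain immunoinflammatory variables related to the use of BCG versus placebo" and, continuing, "among subjects infected and not infected by COVID-19 among the categories with COVID-19 vaccine" (two products are named) and those without it.

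Other text that bears on the objective:

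- **Statistical Analysis Plan, models.** Logistic or robust Poisson regression "will be used to evaluate the effect of BCG vaccine on primary and secondary outcomes". The effect measure is fixed: "Associations will be expressed in the form of risk ratios and respective 95% confidence intervals".
- **Outcomes, item 3.** Within each BCG group, "it will be possible to identify the predictive biomarkers of infection by comparing infected professionals with those who were not infected".
- **Laboratory Procedures.** The cell-profile section relates profiles to infection in both cohorts. The Immunoassays section gives 376 per cohort and sampling at M0, M1, M3 and M12.
- **Study visits table.** Biomarkers are drawn at M0, at M1 (day 10: "Face-to-face visit to the laboratory for blood collection for biomarkers") and, for cases only, 14 to 30 days after symptom onset. The table note restricts them: "Will be performed only in hucff-idt ufrj, HUPE-PPC UERJ centers".
- **COVID vaccination.** Inclusion criterion 4 admits people fully vaccinated at least 15 days before inclusion. The Study visits section lets others be vaccinated after the study dose. The Blinding section allows a placebo recipient, once unblinded on request, to be vaccinated earlier.

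**The concern.** Randomisation makes the two full arms comparable. It does not make infected BCG recipients comparable with infected placebo recipients. If BCG prevents some infections, as the protocol expects, those infected despite BCG are a more selected group than those infected on placebo. A marker related to susceptibility can then differ between them with no BCG effect on the marker at all. The same applies, more weakly, to the uninfected.

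COVID-vaccine category has a similar problem only where vaccination followed the study dose. There, access can depend on the arm through the unblinding provision.

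What is at stake is a primary objective. Followed as written, the plan answers it with several non-randomised comparisons, most of them small, although the scheduled M0 and M1 samples would support a randomised one.

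**Working it through.** **1. Does any other text supply the missing contrast?** The regression sentence nominally covers outcome 3 without conditioning on infection. However, it reports risk ratios from models for binary or count outcomes, which do not fit a marker concentration, and no dichotomy is defined. The text under outcome 3 and in the cell-profile section compares infected with uninfected, so it estimates an association with infection and not an effect of BCG. No text gives BCG versus placebo on a marker in the full arms.

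**2. Reproduce the protocol's expected infections** (Outcomes, item 3). Inputs: 376 per arm; 80% COVID-vaccinated; infection rates 20% (BCG only), 30% (neither) and 15% (COVID vaccine only); joint reduction 10% to 15%.

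- BCG only: 376 × 0.20 × 0.20 = 15.0 (stated 15)
- Neither: 376 × 0.20 × 0.30 = 22.6 (stated 23)
- COVID vaccine only: 376 × 0.80 × 0.15 = 45.1 (stated 45)
- Both: 376 × 0.80 × 0.15 × 0.85 = 38.4 (stated 38; a 10% reduction would give 40.6)

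All four reproduce, the last at the 15% end of the range.

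**3. Stratum sizes.** Each arm has about 75 without and 301 with COVID vaccine. The uninfected follow by subtraction: 75 − 15 = 60 and 75 − 23 = 52; 301 − 38 = 263 and 301 − 45 = 256.

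**4. Smallest detectable difference** in SD units, two-sided 5%, 80% power: 2.80 × √(1/n₁ + 1/n₂).

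| Comparison, BCG vs placebo | n | Share of 752 | Detectable (SD) |
|---|---|---|---|
| Infected, no COVID vaccine | 15 vs 23 | 5% | 0.93 |
| Infected, COVID-vaccinated | 38 vs 45 | 11% | 0.62 |
| Uninfected, no COVID vaccine | 60 vs 52 | 15% | 0.53 |
| Uninfected, COVID-vaccinated | 263 vs 256 | 69% | 0.25 |
| All infected | 53 vs 68 | 16% | 0.51 |
| All uninfected | 323 vs 308 | 84% | 0.22 |
| All randomised | 376 vs 376 | 100% | 0.20 |

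The documents give no immune effect size. For an assumed 0.3 SD, power is 14% and 28% in the two infected strata and 98% for the whole arms.

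**5. Two-centre restriction.** The third centre's share is not stated, so the sizes above are upper limits. If the two biomarker centres recruit two thirds (assumed; 376 × 2/3 ≈ 251 per arm), the whole-arm figure is 2.80 × √(2/251) = 0.25 SD. Every stratum figure grows by the same factor, √(376/251) = 1.22, so the four become about 1.14, 0.76, 0.65 and 0.30 SD.

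**6. Size of the selection effect**, assuming no BCG effect on the marker.

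- *Logistic model, homogeneous effect.* A latent susceptibility with logit slope 0.5 or 1.0 on infection and correlation 0.5 with the marker. Spurious difference among the infected: 0.03 to 0.05 SD at 20% vs 30%; 0.01 to 0.02 SD at the pooled rates (53/376 = 14.1% vs 68/376 = 18.1%); about 0.01 SD at the COVID-vaccinated rates (15% × 0.85 = 12.75% vs 15%).
- *Threshold model (stronger).* Infection occurs when susceptibility exceeds a cut-off. Mean susceptibility of the infected is 1.400 SD at 20% and 1.159 SD at 30%, a gap of 0.241. Times a marker correlation of 0.3 to 0.5, this is 0.07 to 0.12 SD. For the uninfected the gap is 0.147, giving 0.04 to 0.07 SD. At the COVID-vaccinated rates the gap among the infected is 0.083, giving about 0.025 to 0.04 SD.

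**The case against.** The best defence has four parts.

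- **Nothing is thrown away.** A reader might infer that stratifying discards most of the sample. It does not: infected plus uninfected, with plus without COVID vaccine, is everyone. The pooled uninfected comparison detects 0.22 SD, almost as good as 0.20 SD. This stands. The loss is precision within strata, and it is severe only in the three that hold 15% of the sample or less.
- **Other text touches the objective.** A reader might infer that the quoted sentence is the only analysis bearing on objective 3. It is not, as the regression sentence and the infected-versus-uninfected comparisons show. But none of these yields a usable BCG-versus-placebo contrast on a concentration, so the gap remains.
- **COVID-vaccine groups do not always break randomisation.** Vaccination completed before inclusion is a baseline characteristic, and a comparison within that subgroup alone is a randomised one. This stands. The objection to these strata is limited to vaccination after the study dose.
- **The sentence is ambiguous.** It is translated text and may describe how results will be tabulated without excluding an overall contrast. That is possible. Even so, no overall contrast, marker, visit or model is written down, which is not enough for a primary objective.

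**Conclusion.** The concern holds in this limited form: the only immune-specific BCG-versus-placebo analysis for primary objective 3 conditions on a post-randomisation outcome and, for some participants, on post-randomisation COVID vaccination, and no whole-arm comparison of a marker is specified.

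The firmer cost is precision. Three of four strata detect no less than 0.53 SD, against 0.20 SD for the whole arms. These figures rest on the protocol's own infection rates and 80% COVID-vaccine coverage, and on all 752 contributing samples.

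The bias is certain in principle but uncertain in size. A reader might infer that it is large. On the assumptions tried it is about 0.01 to 0.05 SD among the infected, reaching about 0.12 SD only under the stronger threshold model. The documents give no correlation between any marker and susceptibility, so these are illustrations and not estimates. The SAP should be changed, but the trial's data collection is not at fault.

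**What to change.** 1. Make the primary immune analysis BCG versus placebo in all randomised participants with samples at the two biomarker centres, at M1. In the visit table this is the only post-dose biomarker draw scheduled for everyone there (antibody serology is scheduled more often, but is a separate measurement). Analyse the marker as a continuous variable, on the log scale if skewed, by linear model adjusted for the M0 value and centre. If the M0–M1 correlation is 0.5 to 0.7 (assumed), the M0 adjustment cuts variance by 25% to 49% (the squared correlation).
2. Name one primary marker, or state false-discovery control across the listed markers. Roughly 85 are listed, so 0.05 × 85 ≈ 4 false positives would be expected per comparison at 5% if BCG affected none of them.
3. Keep the infection strata, and any strata formed by COVID vaccination after the study dose, as exploratory and labelled non-randomised. COVID vaccination completed before inclusion may stay as a baseline subgroup.
4. Reconcile the Immunoassays section (M0, M1, M3, M12; 376 per cohort) with the visit table, the per-centre laboratory table and the two-centre restriction, and state the number of participants expected to have biomarker data.

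The cost is SAP wording and a small amount of analysis. No extra samples or visits are needed.
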